2.11.2 Sample size for secondary outcomes: growth measures and blood pressure

Four power curves for the secondary outcomes of growth measures and blood pressure, assuming 55%, 60%, 65% or 70% follow-up, are given in Figure 2.11.2. A 2-sided type I error of 5% is used. (A nominal value of $0.05/4 = 0.0125$ was used to control type I error because there are 4 outcomes in this category.) The range of differences for which we have an 80% power is 0.18 to 0.21 standard deviations.

[figure not shown]
Figure 2.11.2 Power Curves for Growth Measures and Blood Pressure

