4ii) *Child Behavior Checklist (CBCL)-Parent Form*: The Parent Form for ages 1½-5 years is used as an additional measure of both attention and behavioural skills.^{47,48} This is one of the most commonly used tools to measure behaviours in children and has been used in studies evaluating behaviours in preterm children. The psychometric properties include high test-retest reliability (0.95-1.0), inter-rater reliability (0.93-0.96), and internal consistency (0.78-0.97) and validity estimates from .55 to .75. The CBCL has undergone numerous studies to assess content and construct validity. Comparisons with clinical status (referred/non-referred) also support the validity of the instrument.^{47,48} The Total Behaviors Problems T scores contributes to the primary outcome. An abnormal outcome is defined as a score that is 1.5 SD above the mean of the normative control sample; again, a higher score reflects abnormality.

The CBCL and BRIEF-P will be made available in all of the languages that are required for the study.

2.8.2 Secondary outcomes for MACS-5:

Secondary outcomes to be assessed in all children include *measures of growth and blood pressure*:

- 1i) height (cm)
- 1ii) weight (kg)
- 1iii) head circumference (cm)
- 1iv) systolic and diastolic blood pressure (mmHg)

Secondary outcomes to be assessed in children in English speaking centres include *intelligence and specific cognitive skills (visual motor, visual spatial, and language skills)*: For logistical reasons, only English-speaking centers that have trained psychologists or psychometrists that are available to administer these more specific psychological tests will participate in these assessments:

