2.10 Will health service research issues be addressed?

An economic analysis will be undertaken as part of *MACS* but is not planned as part of *MACS-5*.

2.11 Sample size and what is the justification for the assumptions underlying the power calculations

[figure not shown]
2.11.1 Sample size for primary outcome: death or survival with a severe disability in at least one of the following domains: neuromotor (non-ambulatory cerebral palsy), neurosensory (blindness, deafness, or need for visual and/or hearing aids), or neurocognitive (abnormal attention, memory or behaviour) function

The sample size of *MACS* is 1900 women. This sample size has an 80% power of finding a 33.3% reduction in the risk of RDS from 12% to 8% (2-sided Type I error of 5%), and greater than 80% power to detect an increase in the incidence of death or neurologic impairment from 5% to 9% at 18 to 24 months corrected age, if such a difference exists (2-sided Type I error of 5%).

We estimate that the children of 55% to 70% of mothers recruited to *MACS* will actually be followed to 5 years of age (or known to have died before this age) (N=1045-1330). This is based on an estimate that 70% to 90% of mothers in *MACS* will be recruited in centres participating in the 5 year follow-up, and that 80% of the children of these mothers will be followed to 5 years of age.

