2.15.2 Analysis of secondary outcomes: growth measures and blood pressure

These secondary outcomes are continuous and will be compared between treatment arms using two-sample t-tests. Multiple linear (least-squares) regression will be used to adjust for the baseline variables. Transformation or ranking procedures will be used if the data are observed to be skewed. A nominal Type I error of 0.0125 will be used to maintain an overall Type I error of 0.05. Since pregnancy is the unit of analysis, the worst value for the children of multiple births will be used.

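### The growth and blood-pressure family is counted as four outcomes but lists five measurements, so the 0.0125 level no longer guarantees the stated overall 0.05 (minor)

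*Protocol*

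**What the plan says.** Protocol Section 2.8.2 numbers four items for growth and blood pressure, 1i to 1iv. The first three hold one measurement each: height, weight, and "1iii) head circumference (cm"). The fourth holds two: "1iv) systolic and diastolic blood pressure (mmHg").

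Section 2.11.2 gives the family level, "A 2-sided type I error of 5% is used", and then explains that 0.05/4 = 0.0125 "was used to control type I error because there are 4 outcomes in this category". The power statement that goes with it is: "The range of differences for which we have an 80% power is 0.18 to 0.21 standard deviations".

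Section 2.15.2 sets the test: "These secondary outcomes are continuous and will be compared between treatment arms using two-sample t-tests". It then makes the claim at issue: "A nominal Type I error of 0.0125 will be used to maintain an overall Type I error of 0.05".

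**The concern.** A Bonferroni divisor has to equal the number of tests in the family. A two-sample t-test takes one variable, so systolic and diastolic pressure need two tests unless something turns them into one. The protocol defines no derived pressure, no joint test and no choice between the two readings. Read as written, the family has five tests, each at a level computed for four.

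The threshold is then slightly too lenient for the error rate attached to it. A p-value between 0.01 and 0.0125 on any of the five measurements would be declared significant under an overall 0.05 that the procedure does not guarantee. Section 1.5 presents the follow-up as determining the safety of repeat courses, and growth and blood pressure are part of that evidence. The number of tests should therefore be settled before the data are seen.

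**Working it through.** **Inputs.**
- Overall two-sided level 0.05, divisor 4, 80% power and 0.18 to 0.21 SD: Section 2.11.2.
- Sample size: Section 2.11.1 expects that the children of 55% to 70% of the 1900 mothers "will actually be followed to 5 years of age (or known to have died before this age) (N=1045-1330").
- Allocation ratio: not stated; 1:1 is assumed.
- Correlations among the five measurements: not given; all values below are assumptions.

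**Step 1. Reproduce the plan's figures.** 0.05/4 = 0.0125, as stated. With 1:1 allocation and SD = 1, the detectable difference is (z for 1 − α/2, plus z for power) × √(4/N). At α = 0.0125 the z-values are 2.498 and 0.842, which sum to 3.339.
- N = 1045: 3.339 × √(4/1045) = 0.207 SD
- N = 1330: 3.339 × √(4/1330) = 0.183 SD

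These round to the stated 0.21 and 0.18. At an unadjusted 0.05 the values would be 0.173 and 0.154, so the divisor of 4 did enter the power calculation. The plan's arithmetic is right; the count is the problem.

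**Step 2. Count the tests.** Height, weight, head circumference, systolic pressure and diastolic pressure make five.

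**Step 3. Family error at 0.0125 per test.**
- Four tests: bound 4 × 0.0125 = 0.05; if independent, 1 − 0.9875⁴ = 0.049.
- Five tests: bound 5 × 0.0125 = 0.0625; if independent, 1 − 0.9875⁵ = 0.061.

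**Step 4. Effect of correlation on five tests at 0.0125.** These are simulated with multivariate normal test statistics, 2 million draws per pattern.

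| Assumed correlation | Family error |
|---|---|
| Common 0.3 | 0.058 |
| Common 0.5 | 0.052 |
| Common 0.6 | 0.048 |
| Only the two pressures correlated, 0.5 to 0.9 | 0.060 to 0.055 |
| Three mixed patterns (growth 0.2 to 0.7, pressures 0.5 to 0.6, across 0.1 to 0.2) | 0.054 to 0.059 |

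With a common correlation the rate crosses 0.05 at about 0.55.

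**Step 5. Level and power for five tests.** 0.05/5 = 0.01, with bound 5 × 0.01 = 0.05 (0.049 if independent). The z-values are 2.576 and 0.842, which sum to 3.417.
- N = 1045: 3.417 × √(4/1045) = 0.211 SD
- N = 1330: 3.417 × √(4/1330) = 0.187 SD

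The restated range is 0.19 to 0.21 SD. The increase is 0.004 to 0.005 SD. A difference that had 80% power at 0.0125 has about 78% at 0.01.

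**The case against.** The strongest reply is that four is a deliberate and consistent count. The secondary research question in Section 1.2.2 asks about height, weight, head circumference and blood pressure. Section 2.8.2 numbers four items, and Sections 2.11.2 and 2.15.2 both use 0.0125. On this view blood pressure is one outcome recorded as two readings, and a statistical analysis plan that is not shown could say how it is tested. This shows that the gap is one of definition rather than of division. It does not remove it: the protocol itself fixes the divisor, the reason for it and the error rate claimed, and its own outcome list does not match the reason. The only combining rule in Section 2.15.2, taking the worst value among children of a multiple birth, merges siblings and not the two pressures. Section 2.11.3 divides by three for three separately named instruments.

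A second reply is that correlated measurements pull the error down, so dividing by four may be close enough. That may be true, but the protocol makes no such argument and rests on the count alone. If only the two pressures are correlated, the error stays above 0.05 even at 0.9.

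A reader might infer that the plan promises strong error control and breaks it, or that the family error certainly exceeds 0.05. The documents support neither. The protocol does not use the term strong control, and under strong correlation throughout the family the rate falls below 0.05.

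It is also fair that in a safety follow-up a missed harm can matter as much as a false signal, and a stricter threshold makes a miss slightly more likely. That bears on the choice of remedy, not on whether the text needs correcting.

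**Conclusion.** The point holds as a minor error. The 0.0125 level was derived for four tests, while the outcome list and the analysis section together imply five. The level therefore does not guarantee the overall 0.05 that Section 2.15.2 states. The guaranteed bound is 0.0625, an excess of at most 0.0125. The error is 0.061 under independence and about 0.048 to 0.058 under assumed moderate to strong correlations, so the true rate may lie slightly above or below 0.05.

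This rests on reading item 1iv as two t-tests, which the text implies but does not spell out. The power figures also assume 1:1 allocation. The matter is confined to secondary outcomes: the primary outcome, its level and its sample size do not change. It does not warrant a must-fix rating.

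**What to change.** Choose one of the following and make Sections 2.8.2, 2.11.2 and 2.15.2 agree.

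1. **Keep both pressures as tested outcomes.** State that there are five outcomes, replace 0.0125 with 0.05/5 = 0.01 (or apply Holm over the five tests), and restate the 80%-power difference as 0.19 to 0.21 SD (0.187 to 0.211). Cost: about 0.005 SD in detectable difference, with no additional participants.
2. **Keep four tests.** Prespecify one blood-pressure measure as the tested outcome and report the other descriptively. The 0.0125 level and the 0.18 to 0.21 SD range then stand. Cost: wording, and no formal test of the second pressure.

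Either choice should be fixed before the treatment arms are compared.

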The primary outcome is a single binary variable, which is “abnormal” for a pregnancy if any child from that pregnancy meets any of the criteria given in Section 2.8.2. We do not know what the risk of an abnormal outcome will be in the placebo group at 5 years of age. However, the Cochrane Review of RCTs of a single course of ACS reports that in the treatment groups, the risk of neonatal death in babies treated after 1980 was 0.084 and the risk of long-term neurological abnormality among survivors was 0.057.⁷ Therefore, we assume that the risk of death or neurodevelopmental morbidity or abnormal cognitive skills (primary outcome) in the placebo arm at 5 years of age is 0.14. Four power curves for the primary outcome, assuming 55%, 60%, 65% or 70% follow-up, are given in Figure 2.11.1. A 2-sided type I error of 5% is used. The range of differences for which we would have an 80% power is 0.059 to 0.067, corresponding to a number needed to treat of 17 to 15. Since we expect to get more than 55%, and perhaps as much as 70%, follow-up at 5 years, we have adequate power for a difference in the range of 0.059 to 0.067, meaning that if physicians are willing to treat up to 15 or 17 patients to prevent an abnormal outcome, then we have sufficient power.

[figure not shown]
Figure 2.11.1 Power Curves for Primary Outcome

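### The detectable range for growth and blood pressure is computed on a follow-up count that includes children who died, so it is slightly too favourable

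*Protocol*

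**What the plan says.** Section 2.11.1 of the protocol starts from the parent trial: "The sample size of *MACS* is 1900 women". It expects that the children of 55% to 70% of these mothers "will actually be followed to 5 years of age (or known to have died before this age) (N=1045-1330"). Deaths therefore count as followed, which is right for a primary outcome of death or severe disability.

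Section 2.11.2 turns to the secondary outcomes: "Four power curves for the secondary outcomes of growth measures and blood pressure, assuming 55%, 60%, 65% or 70% follow-up, are given in Figure 2.11.2". The shares are the same four used for the primary outcome. The test level is 0.05/4 = 0.0125, "because there are 4 outcomes in this category", and the result is: "The range of differences for which we have an 80% power is 0.18 to 0.21 standard deviations".

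Section 2.15.2 gives the matching analysis: "These secondary outcomes are continuous and will be compared between treatment arms using two-sample t-tests". It repeats the level: "A nominal Type I error of 0.0125 will be used to maintain an overall Type I error of 0.05". For multiple births it takes the worst value among the children. It gives no value or rank to a pregnancy in which no child survives.

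Two planning figures in section 2.11.1 bear on how many pregnancies that might be. For the placebo-arm event rate of 0.14, it cites a review of single-course trials in which "the risk of neonatal death in babies treated after 1980 was 0.084". For the parent trial's own 18 to 24 month outcome, it plans on a baseline of 5% for death and neurologic impairment combined.

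**The concern.** A pregnancy whose children have all died is informative for the primary outcome but supplies no height, weight, head circumference or blood pressure. Section 2.11.1 treats deaths as events when it builds the 0.14 rate. Section 2.11.2 then treats the same pregnancies as measurable. The number analysed for growth and blood pressure must be smaller than the number followed, so the detectable differences must be somewhat larger than stated. What is at stake is the accuracy of the stated 80% power for one family of secondary outcomes.

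**Working it through.** **Inputs.** 1900 women and follow-up of 55% to 70%, giving N = 1045 to 1330 (section 2.11.1). Two-sided level 0.0125 and 80% power (section 2.11.2). Two-sample t-test with pregnancy as the unit (section 2.15.2). Equal allocation is assumed, because the ratio is not stated. Figure 2.11.2 is not available in the text, so only the stated range can be checked.

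**Formula.** Detectable difference in SD units, normal approximation: d = (z(1 − 0.0125/2) + z(0.80)) × √(4/N) = (2.498 + 0.842) × 2/√N = 6.679/√N.

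**Reproducing the plan's figures.** N = 1330 gives 6.679/36.47 = 0.183. N = 1045 gives 6.679/32.33 = 0.207. These round to the stated 0.18 and 0.21. The noncentral t gives 0.183 and 0.207 as well. A level of 0.05 gives 0.154 to 0.173 and does not reproduce the range. The stated range therefore corresponds to the count that includes deaths.

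**Removing pregnancies with no survivor.** Let q be the share of followed pregnancies in which no child survives. N is multiplied by (1 − q). Power at the difference that gives 80% on the full count is Φ(3.339 × √(1 − q) − 2.498).

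| q | N at 55% and 70% follow-up | Detectable difference at 70% and 55% follow-up (SD) | Power |
|---|---|---|---|
| 0% | 1045, 1330 | 0.183, 0.207 | 80.0% |
| 2% | 1024, 1303 | 0.185, 0.209 | 79.0% |
| 3% | 1014, 1290 | 0.186, 0.210 | 78.6% |
| 5% | 993, 1264 | 0.188, 0.212 | 77.5% |
| 8.4% | 957, 1218 | 0.191, 0.216 | 75.8% |

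The shift is about 0.003 SD at q = 3% and 0.008 to 0.009 SD at q = 8.4%. After rounding, the lower end becomes 0.19 once q exceeds about 2.0%. The upper end becomes 0.22 only once q exceeds about 7.7%.

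**Which q is plausible.** The protocol does not give it. The 5% baseline for death or impairment is a ceiling on death alone up to 18–24 months; deaths between then and 5 years would be added. The 0.084 is a risk per baby, for neonatal death, from other trials. A multiple pregnancy with one survivor still contributes a value, which lowers q below the per-baby risk; later deaths raise it. So 3% to 5% is taken as the working range and 8.4% as the upper end.

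**The case against.** The strongest reply is that the protocol already has slack. Section 2.11.1 multiplies 70%–90% of mothers by 80% follow-up, which is 56%–72% (N = 1064 to 1368), and then plans on 55%–70%. Starting from the unrounded product and removing 3% leaves 1032 and 1327, with detectable differences of 0.208 and 0.183 SD, which is the printed range. Removing 4% gives 0.209 and 0.184, again the printed range. The sentence giving the 80% also does not say whether deaths lie inside it, and 80% looks cautious beside the 98.6% follow-up reported in section 2.14 for children born in 2001.

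This stands as a reason to call the effect small. It does not remove the point. The rounding is not presented as an allowance for deaths, and it amounts to only about 1.8% (55 against 56) to 2.8% (70 against 72). At 8.4% the unrounded product still gives 0.189 to 0.214 SD. The sentence that produces N = 1045–1330 says in terms that deaths are included.

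A reader might infer that the true range is 0.19 to 0.22 SD. The documents do not establish that: it needs the per-baby risk from other trials to be the share of pregnancies with no survivor, and it sits uneasily with the 5% figure in the same section. A reader might also set power at the rounded differences, 74% at 0.18 SD and 77% at 0.21 SD in the 8.4% case, against the promised 80%. Part of that gap at the lower end is rounding: with no deaths removed, power at 0.18 SD with N = 1330 is already 78%.

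**Conclusion.** The point holds, at minor size. The stated 0.18 to 0.21 SD rests on a denominator that includes deaths, for outcomes that exist only in survivors. The arithmetic on that denominator is correct; the denominator is what needs changing. The detectable differences are understated by roughly 0.003 to 0.009 SD, or about 1 to 4 power points, for q between 3% and 8.4%. With q of 3% to 5% the range is about 0.19 to 0.21 SD. These sizes assume equal allocation and a value of q that the protocol does not state.

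It would go too far to conclude that the follow-up is underpowered. The primary outcome properly counts deaths, the loss is small beside the 55% to 70% spread already shown, and no test or recruitment number changes. Nor is mortality by arm missing: section 2.15.1 already compares the arms on death as a separate domain.

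**What to change.** In section 2.11.2, replace the reused follow-up shares with the expected number of pregnancies that have at least one surviving, examined child. State the assumed share with no survivor and its basis, and restate the detectable range on that number: about 0.19 to 0.21 SD at 3% to 5%, or 0.19 to 0.22 SD at 8.4%. Add a sentence that these comparisons are among survivors and are to be read beside the comparison of deaths already planned in section 2.15.1. Figure 2.11.2 should be redrawn on the same numbers. The cost is a few words and a slightly less favourable figure, with no additional participants.

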2.11.3 Sample size for secondary outcomes: intelligence and specific cognitive skills

We estimate that over 300 women will be recruited in English-speaking centres and that approximately 250 of the children will be followed until 5 years of age. Thus the children of 250 women from participating English-speaking centers will be available to evaluate these outcomes. The power curve for this sample size is given in Figure 2.11.3. The difference for which we have an 80% power is 0.42 standard deviations. For the WPPSI, this corresponds roughly to absolute differences of 5-7 points on the scale.³² (A nominal value of $0.05/3 = 0.0167$ was used to control type I error because there are 3 outcomes in this category.)

Figure 2.11.3 Power Curves for Intelligence and Specific Cognitive Skills

2.12 Recruitment rate

MACS children begin turning 5 years of age in the spring of 2006 and we anticipate that the 5-year follow-up will be completed by December 2011.

2.13 Are there likely to be any problems with compliance?

In *MACS* we regularly assess the rate of compliance with the eligibility criteria and the timing of initial administration of the study drugs for each site and overall. These compliance reports are sent to centres every six months. The most recent overall compliance rate was 92.5%. Additionally, as part of the interim analysis, we looked in depth at the interval between each administration of study drug courses by patient and found a compliance rate of 80.1%.

2.14 Rate of loss to follow-up

We do not anticipate a big problem with loss to follow-up for *MACS-5*, as the follow-up rate for the 18-24 month assessments is 98.6% for children born in 2001. Centres are asked to contact the mothers every 3-6 months, using their judgement as to the best frequency for individual mothers. Only centres committed to the 5-year follow-up are invited to participate in *MACS-5*.

Although this will be the first study of this magnitude to follow children to 5 years of age in so many countries, other studies have also achieved high rates of follow-up for children into school age. Recently, Yeh reported on the outcome at 8 years of age on a cohort of infants who were in their original dexamethasone trial, of whom 61% survived to school age.¹⁵ Of these infants, they were able to report on 92%, reflecting an 8% lost-to follow-up rate. We have based our power calculations on an assumption that we would have outcome information on 55% - 70% of the original sample.

2.15 Analysis

2.15.1 Analysis of primary outcome

Since the pregnancies used for the 5-year follow-up will be a sub-sample of the original *MACS* pregnancies, they will be compared to those not included with respect to the baseline variables: premature rupture of membranes (PROM), multiple birth (1 fetus versus 2+) and gestational age at randomisation. In addition, in the sample used for the 5-year follow-up, the treatment arms will be compared with respect to the same baseline variables. Fisher's exact tests will be used for PROM and multiple birth, and t-tests (or Mann-Whitney U test, if data are skewed) for gestational age. A two-sided Type I error of 0.05 will be used.

The primary outcome will be compared between treatment arms using a Fisher's exact test with a two-sided Type I error of 0.05. The relative risk and its corresponding 95% confidence interval will be calculated. In addition, a logistic regression analysis will be performed to compare treatment arms while controlling for PROM, multiple birth and gestational age. A multi-level model will be applied to the data using WinBUGS (version 1.4.1, see www.mrc-bsu.cam.ac.uk/bugs/welcome.shtml) to allow for random effects (intercept and slope) due to centres while also controlling for baseline variables. Using a similar analytic approach, a supportive analysis as described in the above four sentences will compare treatment arms with respect to the four domains comprising the primary outcome (death, neuromotor disability [non-ambulatory cerebral palsy], neurosensory disability [blindness, deafness, or need for visual and/or hearing aids], and abnormal cognitive score). Since pregnancy is the unit of analysis, if any child of a multiple birth has an abnormal outcome, the pregnancy will be considered to have had an abnormal outcome. If some of the data are missing, the child will only be considered to have an abnormal outcome if he or she is abnormal based on the data that are not missing.

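### The missing-data rule for the primary outcome in effect scores a survivor without a BRIEF-P or CBCL as not abnormal, which dilutes the safety comparison

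*Protocol*

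**What the plan says.** Section 2.8.1 of the Protocol defines the primary outcome as death or severe disability in a neuromotor, neurosensory or neurocognitive domain. The neurocognitive domain rests on two parent-completed instruments, the BRIEF-P and the CBCL, and the section names neurocognitive function as the main aim of the follow-up.

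Section 2.15.1 fixes the rule for incomplete data: the child "will only be considered to have an abnormal outcome if he or she is abnormal based on the data that are not missing". It also makes the pregnancy the unit of analysis, abnormal if any child is abnormal. Section 2.11.1 describes the outcome as one binary variable. Neither section provides a category for children who cannot be classified.

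On who is available, section 2.11.1 counts children who "will actually be followed to 5 years of age (or known to have died before this age) (N=1045-1330") and assumes that "80% of the children of these mothers will be followed to 5 years of age" in participating centres. Section 2.14 repeats that "we would have outcome information on 55% - 70% of the original sample".

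**The concern.** A binary outcome with a rule only for when an incomplete child is abnormal leaves one natural reading: every other incomplete child is not abnormal. A child seen by the clinician, with no cerebral palsy and no sensory loss, but whose parent returned no form, then counts as a good outcome. The component most exposed to this is the one the study was set up to measure.

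False normals of this kind shrink the difference between arms even when they are equally common in both. Section 1.5 says the study will determine the safety of repeat courses and inform guidelines, so an error toward no difference is an error toward reassurance.

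A second, related point is less explicit. A known death can always be classified, whereas a survivor lost to follow-up has no 5-year outcome. If lost survivors leave the analysis, deaths carry more weight in the analysed set than in the randomised population.

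**Working it through.** **Inputs.** From section 2.11.1: placebo risk 0.14; detectable differences 0.059 (N=1330) to 0.067 (N=1045) at 80% power; two-sided alpha 0.05; neonatal death risk 0.084; neurological abnormality among survivors 0.057; 80% followed. Assumed: 1:1 allocation; these risks applied per pregnancy; the share *m* of disabled survivors who are missed.

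**1. The plan's own figure.** With *n* = N/2 per arm and a continuity correction,

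power = Φ{[Δ − 1/n − 1.96·√(2p̄(1−p̄)/n)] / √[(p₀(1−p₀)+p₁(1−p₁))/n]}.

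For 0.14 vs 0.199 and n = 665: (0.059 − 0.0015 − 0.0403)/0.0205 = 0.84, so power is 79.9%. For 0.14 vs 0.207 at N=1045 it is 79.4%. The stated range reproduces as an increase in risk. As a decrease from 0.14, power would be 91.8% and 92.8%. Section 2.11.1 words the difference as prevention, but the increase is what its figures support and is also the safety direction, so it is used below.

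**2. Missed disability.** Deaths cannot be missed for want of a form, so only the disability part, 0.14 − 0.084 = 0.056, is reduced. The observed placebo risk is 0.084 + 0.056(1−m).

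- All harm in disability: observed treated risk = 0.084 + (0.056 + 0.059)(1−m).
- Harm proportional over death and disability: observed treated risk = observed placebo risk × 0.199/0.14.

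At N=1330:

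| m | Placebo | Treated, all disability | Difference | Power | Treated, proportional | Difference | Power |
|---|---|---|---|---|---|---|---|
| 0 | 0.140 | 0.199 | 0.059 | 80% | 0.199 | 0.059 | 80% |
| 5% | 0.137 | 0.193 | 0.056 | 76% | 0.195 | 0.058 | 79% |
| 10% | 0.134 | 0.188 | 0.053 | 73% | 0.191 | 0.057 | 78% |
| 20% | 0.129 | 0.176 | 0.047 | 64% | 0.183 | 0.054 | 76% |

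At N=1045 (difference 0.067), m = 10% (20%) gives 72% (64%) with all harm in disability and 77% (75%) with proportional harm.

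**3. No treatment effect.** With the same *m* in both arms, the two observed risks are equal, so type I error is not inflated.

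**4. Lost survivors.** Let *d* = 0.084, *s* = 0.057 and *r* be the share of survivors followed, with all deaths known. Observed risk = [d + (1−d)rs] / [d + (1−d)r].

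- r = 1: 0.084 + 0.916×0.057 = 0.136.
- r = 0.80: (0.084 + 0.0418)/(0.084 + 0.7328) = 0.154; deaths are 0.084/0.8168 = 10.3% of the analysed set instead of 8.4%.
- If the 80% includes known deaths, r = (0.80 − 0.084)/0.916 = 0.78 and the observed risk is 0.156.

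**The case against.** The strongest reply is that section 2.15.1 says only when an incomplete child is abnormal; it never says the others are normal. That is literally true. But a binary outcome with no third category leaves no other place for them, and if another reading was meant the rule needs rewriting anyway.

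Several further objections stand and limit the point:

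- **Unseen twin.** A reader might infer that one normal and one unseen twin make a normal pregnancy. The rule covers a child with some data missing, not an unseen child, so this case has no stated rule.
- **Analysis set.** That lost survivors drop out is inferred from the planning sentence in section 2.11.1. Section 2.15.1 does not define the set for children with no 5-year data, and a separate analysis plan may.
- **Hidden trade-off.** A reader might infer that fewer deaths could conceal more disability. Section 2.15.1 plans a comparison of arms on each domain, which would show opposing effects, although the neurocognitive domain would be diluted there too if the same missing-data rule is applied.
- **Spurious difference.** Unequal form completion could create one, but no document gives unequal rates. Masking of parents and caregivers (section 2.4), staff help with the forms (section 2.9) and translated versions (section 2.8.1) make a large imbalance less likely.
- **Earlier outcomes.** Section 2.14 says "the follow-up rate for the 18-24 month assessments is 98.6% for children born in 2001". That is one birth year in a trial still enrolling, and does not show near-complete data for all the children.

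It is also tempting to scale the whole composite, which gives 74.5% (68.3%) power for 10% (20%) missed. That lets deaths be missed. Missing 10% of all abnormal placebo pregnancies would require 0.014/0.056 = 25% of the disabled ones to be missed.

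**Conclusion.** The point holds for the classification rule. As written, it in effect turns missing neurocognitive data into normal outcomes and biases the primary comparison toward no difference. The loss is modest to material: with 10–20% of disabled survivors missed, power at N=1330 falls from 80% to 73–64% if all the harm is in disability, and to 78–76% if it is proportional. The miss rates are assumptions. They describe disabled children who go undetected, which will be fewer than those with a missing form, because a child abnormal on any observed component is still classified correctly.

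The documents do not support a claim of inflated type I error, or of a false difference between arms. The over-weighting of deaths (placebo risk 0.154 rather than 0.136) is a secondary point that depends on the inferred analysis set. With equal survivor follow-up and no treatment effect, it does not by itself create a difference.

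**What to change.** Replace the rule in section 2.15.1 before the single final analysis:

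1. A pregnancy is abnormal if any observed component in any child is abnormal; normal only if every component is observed normal in every child; otherwise missing. This also settles the unseen twin.
2. Multiply impute the missing components from arm, centre, gestational age, PROM, plurality, the observed components and whatever 18–24 month MACS outcomes are available. Extend the imputation to lost survivors in participating centres.
3. Make the already planned logistic model, pooled over imputations, the primary analysis. Keep the current rule with Fisher's exact test as a sensitivity analysis.
4. Do not analyse the reclassified data as complete cases. Abnormal children with partial data would stay in while non-abnormal ones with the same gaps were dropped, which would bias the risk upward.

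No new data are needed. The costs are extra programming, reliance on the imputation model, and a pooled model in place of Fisher's exact test as the primary test.
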